Our previous feasibility study demonstrated that our novel LTTT for DUs was safe, feasible, and well tolerated. Furthermore, there was an early tentative suggestion of treatment efficacy. There is a significant therapeutic rationale to develop locally acting treatments for SSc-DU, which likely would be better tolerated by patients, and could be administered potentially in the community (our outpatient setting under medical supervision), thereby avoiding the costs and inconvenience from inpatient hospitalisation. Furthermore, many previous studies have found comparable efficacy at lower doses (total dose 5 to 10 J/cm²). Although, some studies have also found positive results with much higher doses, such as 20J/cm², 70J/cm², or even higher.

However, a biphasic response to light is well known, and therefore there is a need to scientifically determine the dose-ranging of LLLT for SSc-DU, including examination of potential patient- and disease-related factors.

4 Objectives

Primary Objective: To assess the safety, tolerability, and efficacy (as assessed by surrogate measurement of skin perfusion and temperature) of our LLLT (combined red, infrared and violet wavelengths) concerning dose finding with lower and higher irradiances, including evidence of a biphasic response with higher irradiance dose.

Secondary Objective: To investigate potential SSc patient- and disease-related factors relevant to cutaneous irradiation with LTTT.

- Age and disease duration.
- Skin thickness.

5 Study Design

A physiological, clinical laboratory-based, study of LLLT.

LTTT experimental setup

A new LTTT device (Figure 2) shall be constructed in-house by Medical Physics at Salford Royal Hospital and subject to appropriate safety and quality assurance checks.

Allocation of LLLT intervention

Prior to the initial study visit, an independent member of the study team shall perform the randomisation procedure. Randomisation to be done in house by study team (e.g., using random number generator/excel). All patients shall receive combined sequential red (810nm)/infrared (850nm) followed by blue (410nm) wavelengths. The dose per visit shall be dose-escalated in a pre-determined randomised order over the course of the three study visits: 5 J/cm² or 10 J/cm² (i.e., the dose of our previously explored LLLT), and 20 J/cm²

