At each treatment study visit any safety issues (between visits) will be documented (e.g., new concerns about cutaneous changes). This will be documented on a separate safety CRF at visits 2 and 3 (attached with this application). Patient reported pain on a VAS scale (0-100, where 100 is the most severe pain imaginable by

the patient) directly attributed to the LLLT will be recorded immediately after treatment, on a separate tolerability CRF at visits 1, 2 and 3 (attached with this application), to assess tolerability, at each study visit.

Assessment of efficacy

Laser Doppler imaging (LDI); LDI which measures blood flow allows a perfusion map (in arbitrary units) to be produced of the studied area. We will perform LDI immediately before and after the light exposures and then every 10 minutes for 90 minutes. LDI will include all the digits (thumb and four fingers) and dorsum of both the *treated* and *untreated* hands. Bilateral (matching) standard regions of interest (ROI) shall be assessed on the treated and untreated hands all LDI time points. The rationale of imaging these sites is to demonstrate an objective *localised* increase in skin perfusion with light treatment, and whether this differs between the digits and dorsum of the hand.

Thermography: Thermographic assessment measures skin temperature and provides an indirect measure of small and large blood vessel function and can also be applied to SSc-DUs. Standardised thermographic images shall be acquired immediately before and after the light exposures, and then every 10 minutes for 90 minutes. As for LDI, thermography will simultaneously image the whole treated hand to capture the fingers and dorsal aspect, and with contralateral counterparts on the untreated hand.

Assessment of persistent cutaneous digital ischaemia

Taken from the hand original acquired LDI and thermography images (as above), for any digital (finger) ulcers (DU) or pitting scars (DPS) present, perfusion measurements will be assessed at the lesion center (DU/DPS 'core') and immediately adjacent tissue (DU/DPS 'periphery').

Assessment of digital skin fibrosis:

Rodnan skin score: By a trained assessor using the modified Rodnan skin score by manual palpation (0-3 score, where 0 is normal and 3 is severe skin fibrosis/sclerosis).

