6.4 Study Duration

The study will recruit for a I year period with a proposed start date of 14/02/2025 with a recruitment end date of 13/02/2026 and a study end date (last patient, last visit) of 20/02/2026. Patients will attend a total of 3 study (morning) visits over 3 (ideally consecutive) days. The minimum time between study visits is 1 day, and the maximum time between study visits shall be 3 days. The patient will therefore be in the study between 3 days and 7 days. Study visits will last approximately 2 hours. We will aim to complete study write up within 12 months of the study ending. The study end date will be defined as the last study visit of the last participant recruited.

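### No safety check is scheduled after visit 3, so one exposure in three has no record of delayed reactions, although safety is part of the primary objective

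*Protocol*

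**What the plan says.** Section 4 puts safety in the primary objective, alongside tolerability and surrogate efficacy, in a dose-finding setting: "Primary Objective: To assess the safety, tolerability, and efficacy (as assessed by surrogate measurement of skin perfusion and temperature) of our LLLT".

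Section 5, under the assessment of safety and tolerability, defines what is recorded and when:

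- Scope: "At each treatment study visit any safety issues (between visits) will be documented (e.g., new concerns about cutaneous changes".
- Timing: "This will be documented on a separate safety CRF at visits 2 and 3 (attached with this application".
- Tolerability is separate: a pain VAS "directly attributed to the LLLT will be recorded immediately after treatment, on a separate tolerability CRF at visits 1, 2 and 3".

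Under the assessment of efficacy, imaging continues after each exposure: "We will perform LDI immediately before and after the light exposures and then every 10 minutes for 90 minutes". Thermography follows the same schedule.

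Section 6.4 sets the calendar: "Patients will attend a total of 3 study (morning) visits over 3 (ideally consecutive) days". Visits are 1 to 3 days apart, and each patient is in the study for 3 to 7 days. It closes the study as follows: "The study end date will be defined as the last study visit of the last participant recruited".

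Section 5 also says that one of three doses (5, 10 or 20 J/cm²) is given at each visit, in an order set by randomisation, and that the same hand is treated throughout, normally the dominant one.

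**The concern.** The safety form looks back over an interval. At visit 2 it covers the time since the first exposure, and at visit 3 the time since the second. No later form or contact covers the time since the third. The protocol treats a between-visit skin check as needed after the first two doses, and gives no reason for leaving it out after the last.

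The missing interval matters in two ways. For every patient it is the only one that follows all three doses on the same hand (5 + 10 + 20 = 35 J/cm² in total), possibly on consecutive days. It also removes part of the safety information on each dose, in a study that sets out to compare doses. A conclusion of no safety concerns would then rest on incomplete follow-up, and no analysis can recover data that were never collected. Section 8.4 would halt the study if safety issues come to light, but a delayed reaction after visit 3 has no scheduled route by which to do so.

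**Working it through.** **Is there any time after visit 3?** Visit 3 falls on day 1 + 2 × gap.

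- Gap of 1 day: 1 + 2 × 1 = day 3.
- Gap of 3 days: 1 + 2 × 3 = day 7.

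This reproduces the 3 to 7 days in Section 6.4 exactly, so stated participation ends at visit 3. The calendar dates agree: recruitment closes on 13/02/2026 and the study on 20/02/2026, 7 days later. Visit 1 to visit 3 takes up to 6 days, which leaves at most one day spare, and the text assigns no contact to it.

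**Exposures with a later safety record.** This assumes that all 20 patients complete three visits.

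- Exposures: 20 × 3 = 60.
- Followed by a safety form: 20 × 2 = 40.
- Not followed: 60 − 40 = 20, or 33%.

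Under Sections 5 and 6.5, a patient who withdraws after visit 1 or 2 has no further visits or data collection, so would also lack a record for the last exposure received. The followed share would then be lower.

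**How the loss falls by dose.** A dose loses its delayed record in each patient who receives it last.

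- Balanced sequences: 20 / 3 = 6.7 patients per dose, so 6-7 unfollowed and 13-14 followed.
- Simple randomisation: Section 5 mentions only a random number generator or spreadsheet and describes no balancing. The number receiving a given dose last is then Binomial(20, 1/3), with a central 95% range of 3 to 11. That leaves 20 − 11 = 9 to 20 − 3 = 17 followed.

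**What zero events would show.** With no events in n followed patients, the one-sided 95% upper bound on the event rate is 1 − 0.05^(1/n).

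| Followed at a dose | Situation | Upper bound |
|---|---|---|
| 9 | simple randomisation, low end | 28.3% |
| 13 | balanced order | 20.6% |
| 14 | balanced order | 19.3% |
| 17 | simple randomisation, high end | 16.2% |
| 20 | all exposures followed | 13.9% |

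The protocol states no safety precision target or event-rate threshold, so there is no planned figure to compare these with.

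**The case against.** **The visit 3 exposure is not unobserved.** A reader might infer that the last dose is given with no safety information at all. The text does not support that. There is a pain score straight after treatment, and the treated hand is imaged for 90 minutes with the patient attending. This stands, and it limits the point to what happens after the patient leaves. Those measurements are assigned to tolerability and efficacy, and they stop too early to show the delayed skin changes the safety form asks about.

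**The highest dose is not singled out.** One sentence in Section 5 describes the doses as escalated. A reader might infer that 20 J/cm² always comes last, so that none of its 20 exposures would be followed. But the same sentence says the order is randomised, the lay summary says patients will not all have the same order, and the device section ties each dose to the patient's randomised sequence. The 20-of-20 case is therefore not supported. The wording conflict is a separate matter.

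**The record is incomplete.** Figure 3 (participant progression) and the safety form are not shown. The absence of a later contact is an inference from the text, though Section 6.4 points firmly that way.

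**The gain in precision is modest.** Upper bounds of about 20% and 13.9% are both uninformative about uncommon reactions. The main limit is 20 patients, in a physiological study meant to inform a later feasibility trial. This stands, and it argues against treating the gap as fatal.

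**Earlier data help in part.** The previous study gave 46 exposures at 10 J/cm², followed patients to weeks 4 and 8, and reported no safety concerns. That bears on the middle dose. It does not cover 20 J/cm² or the new sequential set-up with a different blue wavelength.

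**Conclusion.** The point holds in a limited form. On the visible text, no safety check is scheduled once the patient leaves visit 3, so 20 of 60 planned exposures (33%) have no delayed safety record. These include, for every patient, the interval after all three doses have been given to the same hand.

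The loss is shared among the doses. Per dose it is about 6-7 of 20 with balanced sequences, an assumption the protocol does not guarantee, and roughly 3-11 of 20 under simple randomisation. In the balanced case a zero-event result bounds a dose's event rate at about 19-21%, where complete follow-up would give 13.9%.

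This rests on all patients completing three visits and on no later contact appearing in the unseen figure or form. It is a gap against the primary objective that is worth closing before data are lost. It does not invalidate the study.

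**What to change.** Add one telephone contact 1-3 days after visit 3, matching the existing between-visit window, and complete the existing safety form at that contact. In Section 6.4, move each patient's end of participation, and the study-end definition, to that contact. Delayed safety records would then cover 60 of 60 exposures instead of 40.

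Report safety by most recent dose, with two stated limits. The record after visit 3 follows cumulative exposure to all three doses, so it cannot isolate the effect of the last one. A call also relies on the patient's own report, without inspection of the skin. Completing the form at the end of visit 3 instead would add little, because 90 minutes is too soon for the delayed changes in question.

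The cost is 20 short calls by the existing team, a small amendment, and a study end up to 3 days later.

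Separately, the description of the doses as escalated and of their order as randomised, in the allocation paragraph of Section 5, must be reconciled.

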Participants will not be paid to take part in the study; however, they will be reimbursed reasonable travelling expenses for each of their 3 study visits

[figure not shown]

Figure 3. Participant progression throughout the study. We assume no significant therapeutic carry over effect between the LLLT irradiation between study visits (minimum of 24 hours).

Preparation

Patients will be asked to abstain from caffeine-containing drinks and from smoking for at least 4 hours prior to study.

Clinical data

After signing the informed consent form, the patient will be interviewed by a member of the study team using a standard proforma and/or standardised proformas.

This will include:

- Demographic information.
- Gender.
- Age.
- Smoking status
- Fitzpatrick skin type/colour (for potential effects of melanin).
- Modified Rodnan skin score assessment
- Current medication/s.
- Past medical history.
- Disease-related history (e.g., history of severe digital vascular disease).
- Record of ulcers present and past and also of location, duration etc.
- Handedness (i.e., dominant hand).

Application of the LLLT device

We will apply the LLLT (for all study visits) to the dominant hand unless there are specific reasons not to, which will be documented. For example, due to patient preference or major musculoskeletal involvement with upper limb disability/contractures prohibiting correct positioning for the application of the LLLT.

Both the patient and device operator/s will wear appropriate safety goggles (as advised by Medical Physics at Salford Care Royal Hospital) at all times whilst the LLLT device is in operation. The patient will place their hand within the treatment area of the light-based device (total treatment area of approximately 15cm²), aiming to centralise the hand (fingers/thumbs and dorsal aspect) within the treatment region. The device will be directly controlled by an attached custom-built computer interface. At each study visit, the device will undergo a period of automatic calibration before use.

Using the custom interface/s, the dose of the wavelengths can be selected to be delivered as prior study. The dose will be delivered either at 5 J/cm², 10 J/cm² or 20 J/cm² based upon the patient study visit sequence/randomisation. The LLLT will take approximately 10-15 minutes to complete.

Outcome measures

Assessment of safety and tolerability

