All confidential data will be kept in a locked file room and electronic data will be password protected where only the Investigator and delegated staff have access.

After consent is obtained, patients will be given a unique code that will be used for data acquisition and analysis.

Pseudonymised data will be analysed on NHS or University computers by members of the research team.

Statistical advice/support will be provided by Research & Innovation, Northern Care Alliance NHS Foundation Trust, [name].

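### The protocol does not say who places the image regions or that this reader is masked to dose and visit, so the between-dose imaging comparison may be read by people who know the dose.

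*Protocol*

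**What the plan says.** All places are in the Protocol.

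- **Objective (section 4).** Efficacy, measured through skin perfusion and temperature, is part of the primary objective. That objective is about dose finding, including a possible biphasic response. The lay summary (section 2) states that there is no placebo.
- **Allocation (section 5, Allocation of LLLT intervention).** "Prior to the initial study visit, an independent member of the study team shall perform the randomisation procedure". The next sentence adds: "Randomisation to be done in house by study team (e.g., using random number generator/excel".
- **Dose delivery (section 5, Application of the LLLT device).** "Using the custom interface/s, the dose of the wavelengths can be selected to be delivered as prior study".
- **Hand regions (section 5, Assessment of efficacy).** "Bilateral (matching) standard regions of interest (ROI) shall be assessed on the treated and untreated hands all LDI time points". Thermography covers the same sites on both hands.
- **Lesion regions (section 5, Assessment of persistent cutaneous digital ischaemia).** The source is stored material: "Taken from the hand original acquired LDI and thermography images (as above". From it, "for any digital (finger) ulcers (DU) or pitting scars (DPS) present, perfusion measurements will be assessed at the lesion center" (the core) and in the tissue next to it (the periphery).
- **Analysis (section 7.2).** An area under the curve is calculated per patient for flow or temperature and compared with a t-test. Pain VAS scores are explored graphically.
- **Data handling (section 8.5).** "Pseudonymised data will be analysed on NHS or University computers by members of the research team". Section 7.2 gives coding and de-identification to the study team.

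**The concern.** The imaging devices give a map. A person, or a rule, turns the map into a number by deciding where the region lies. On a heterogeneous perfusion map, moving or resizing a region changes its mean. If the reader knows which dose was given, any tendency to favour one dose enters the contrast between 5, 10 and 20 J/cm² directly. Without a placebo arm, that contrast is the only randomised comparison in the study.

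The protocol describes its choice of imaging sites as a way to show an objective, localised rise in perfusion. Nothing written protects that objectivity at the reading step. Masking also has to be arranged before the images are read. It is a matter of conduct, and a later analysis plan cannot restore it once regions have been placed with the dose in view.

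**Working it through.** The protocol gives no figure for reading error or bias, so there is nothing to reproduce. The check sets the passages side by side and then counts the readings.

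**1. Who knows the dose?** The order is generated by a member of the study team described as independent. The dose is then selected on the device interface, so whoever operates the device knows it. Nothing says that the randomisation list is withheld from anyone else.

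**2. Who places the regions?** No reader is named for the hand regions or for the lesion regions. The nearest statement is the one in section 8.5 that research team members analyse the data. Overlap between operator and reader is therefore possible. It is not stated.

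**3. Is the reader masked?** Blinding is mentioned only for other studies: one trial described in section 3, and titles in the reference list. Pseudonymisation in section 8.5 replaces participant identity with a study code. It is not said to hide dose, visit or time point.

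**4. How much discretion does the reader have?**

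| Outcome | Rule given | Discretion left |
|---|---|---|
| LDI, digits and dorsum | Standard regions, matched across hands, used at all time points | Some: exact placement is not described |
| Thermography, same sites | Same sites imaged on both hands; no region rule of its own | Some |
| Lesion core and periphery | Lesion centre and adjacent tissue; no size or boundary | Most |

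**5. How many readings are exposed?**
- Time points per visit: 1 before + 1 immediately after + 9 (10 to 90 minutes in steps of 10) = 11.
- Per patient: 11 x 3 visits = 33.
- In total: 33 x 20 patients = 660 occasions for LDI, and the same for thermography, each covering both hands.

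The count shows how much reading takes place without stated masking. It is a workload and does not measure bias.

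**6. Could the reading be masked?** Yes for the lesion readings, which are expressly taken from images already acquired. The hand regions can be handled in the same way if they too are placed on stored files.

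**The case against.** The strongest reply is that the main outcome is better protected than the concern suggests. The hand regions are standard, matched across hands and applied at every time point, they cover fixed anatomical sites, and an untreated hand is imaged alongside. The perfusion and temperature values come from instruments. The loosely defined core and periphery apply only to patients with lesions, and lesions are not an inclusion criterion, so an unknown share of the 20 contributes. This stands as a limit on the risk for the hand regions, but it does not remove the risk.

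Three stronger readings are tempting and are not supported:

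- **That the people who set the dose also mark the images.** A reader might infer this from the analysis sentence in section 8.5. That sentence concerns data protection, and the dose-selection sentence names no operator. The documents allow overlap without stating it.
- **That the bias can be sized against the 15-32% perfusion rise in section 7.2.** That figure is a rise after irradiation in the earlier study of 14 ulcers in eight patients, treated at 10 J/cm² (section 3). It is not a difference between doses. Bias in the dose contrast would require placement to differ by dose, and nothing in the documents quantifies that.
- **That the pain VAS is equally exposed.** The protocol does not say whether patients know the dose. However, the scores are only plotted, the earlier mean was 1.6 on a 0-100 scale (SD 5.2), and the patient-facing forms are not shown. This is a minor point.

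It can also be said that a 20-patient physiological study, meant to inform a later feasibility trial, needs less protection. That argues for a light remedy, and the remedy here is light.

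**Conclusion.** The point holds in this form: the protocol names no reader for the LDI, thermography and lesion regions and states no masking of that reader to dose or visit. As written, it permits dose-aware reading of the efficacy part of its primary objective. The exposure is greatest for lesion core and periphery, where no boundary rule is given, and smaller for the standard matched regions. The amount of bias, if any, cannot be derived from the documents.

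The conclusion assumes that region placement involves some human judgement, which the protocol neither states nor excludes. If placement were fully automatic, little of the concern would remain for the hand regions. The correction is worth making because it is cheap and cannot be made after the images have been read.

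**What to change.** Add to section 5, under the outcome measures:

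1. The independent team member who prepares and holds the randomisation list recodes the stored LDI and thermography files so that dose and visit number are hidden. The code is opened only when all regions are final.
2. The existing reader places regions by a written anatomical-landmark rule, including a size and boundary for lesion core and periphery. Regions are set on the pre-light image and realigned to the same landmarks on the ten later images of that visit. Copying them unchanged would not do, because the hand goes into the light device after the first scan and may move over the following 90 minutes.
3. As a minor addition, patients are not told the dose before they give the pain VAS.

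The cost is a few hours of file recoding within the existing team, with no extra reader, visit or patient. Two limits remain and should be stated: the device operator stays unblinded, and time point is not masked, because the pre-light image is identified as such.
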